---

**DOCUMENT VERSION HISTORY**

Date	Version	Reason for Revision
17/10/2022	1.0	Initial
10/07/2023	1.1 SWE	
Updates as per request from the Regulatory Authorities and Ethics Committees from several countries
 
Minor grammatically changes and correction of inconsistencies.
 
Updates in the wording of several sections for better understanding
 
Corrected typos: CSF, Screening
 
3.2.2 Updates in the wording of endpoint for survival
 
3.2.2 Addition of secondary endpoint (SVC)
 
4. Updated wording about study duration
 
5.2 Updates in wording of incl. criteria. Addition of wording about inc/excl criteria for patients only in follow up for vital status
 
5.3 Addition of exclusion criteria section
 
6 (Table 1): clarification (footer) for patients only in vital status FU, Addition of lab parameters in footer of table 1 in line with table 2.
 
6. Addition of wording about participants follow up in case not attending site visits
 
6.1 Section re-worded to clarify baseline assessments of the main study can be used.
 
6.2&6.3: updates to align with Table 1
 
6.4 New section added to clarify procedures for patients only in vital status follow up
 
6.5. Discontinuation criteria updated
 
7.1.2 typo in compliance corrected (100%)
 
7.1.3 IMP shipment re-worded
 
9.8 section updated in line with 6.5
 
11.3.1 added wording to clarify analysis
 
11.3.4 added wording to clarify analysis
 
11.3.4 SVC added in the analysis

## ABBREVIATIONS

3-NT	3-Nitrotyrosine
4HNE	4-hydroxy-2-nonenal
8-OHdG	8-hydroxyguanosine
ADR	Adverse Drug Reaction
AE	Adverse Event
AIS	Acute Ischaemic Stroke
ALS	Amyotrophic Lateral Sclerosis
ALSFRS-R	ALS Functional Rating Score – revised
ALSAQ-40	ALS Assessment questionnaire 40
ALT	Alanine transaminase
aPTT	Activated partial thromboplastin time
AST	Aspartate transaminase
AUC	Area Under the Curve
BID	Twice Daily
BUN	Blood urea nitrogen
CAFS	Combined Assessment of Function and Survival
CAS	Chemical Abstracts Service
CHMP	Committee for Human Medicinal Products
CI	Confidence Interval
CK	Creatinine kinase
C max	Maximum concentration
CNS	Central Nervous System
CYP	Cytochrome P450
CV	Coefficient of Variation
DSMB	Data Safety Monitoring Board
EC	European Committee
ECAS	Edinburgh Cognitive and behavioural ALS Screen
eGFR	Estimated glomerular filtration rate
EMA	European Medicines Agency
EMG	Electromyography
EQ-5D-5L	EuroQoL – 5 Dimensions – 5 Levels
fALS	familial Amyotrophic Lateral Sclerosis
FBR	Future Biomedical Research
FDA	Food and Drug Administration
FAB122	Ferrer New Product 122* (FNP122)
FTD	Frontotemporal dementia
FVC	Forced Vital Capacity
G93A	G93A-human Cu/Zn superoxide dismutase

GGT	Gamma-glutamyl transpeptidase
GI	Gastrointestinal
HCT	Haematocrit
HEK	Human Embryonic Kidney
hERG	human Ether-a-go-go-Related Gene
Hgb	Haemoglobin
hOAT	Human Organic Anion Transporter
HSP	Hereditary Spastic Paraparesis
IC 50	Half Maximal Inhibitory Concentration
IDMC	Independent Data Monitoring Committee
INN	International Non-proprietary Name
iNOS	Inducible Nitric Oxide Synthase
IV	Intravenous
IUPAC	International Union of Pure and Applied Chemistry
Km	Michaelis constant
LD 50	Median Lethal Dose
LDH	Lactate dehydrogenase
LMN	Lower Motor Neurons
MMRM	Mixed Model for Repeat Measures
MND	Motor Neuron Disease
MoA	Mechanism of Action
MOS	Margin of Safety
mSOD1	Mutated Superoxide Dismutase 1
MVV	Maximum Voluntary Ventilation
NAA	N-Acetyl Aspartate
NCS	Nerve Conduction Study
NF	National Formula
NFL	Neurofilament Light
NIPPV	Non-invasive Positive Pressure Ventilation
NMR	Nuclear Magnetic Resonance spectroscopy
NOAEL	No Observed Adverse Effect Level
Nrf2	Nuclear erythroid 2-related factor 2
OAT	Organic Anion Transporter
OD	Once Daily
OLE	Open-label extension
P75 EDC	Extracellular domain of neurotrophin receptor p75
PAP	Pharmacokinetics Analysis Plan
PEG	Percutaneous Endoscopic Gastrostomy
PEG 400	Polyethylene glycol 400
PK	Pharmacokinetic(s)
PLP	Pyridoxal Phosphate

PLS	Primary Lateral Sclerosis
PMM	Pattern Mixture Model
PNS	Peripheral Nerve System
POC	Proof of concept
PTT	Prothrombin Time
Q1, Q3	First quarter, third quarter
QoL	Quality of Life
RBC	Red blood cell
RDW	Red cell distribution width
RNA	Ribonucleic acid
ROS	Reactive Oxygen Species
SAE	Serious Adverse Event
sALS	Sporadic Amyotrophic Lateral Sclerosis
SAH	Subarachnoid Haemorrhage
SAP	Statistical Analysis Plan
SD	Standard Deviation
SLS	Sodium Laurilsulfate
SOC	Standard of Care
SOD1	Superoxidase Dismutase 1
SULT	Sulfotransferase
SVC	Slow Vital Capacity
$t_{1/2}$	Half-life
TDP-43	Transactive response DNA/RNA Binding Protein 43
TEAE	Treatment Emergent Adverse Event
TID	Three Times Daily
$t_{max}$	Time to peak concentration
TW	Treeway
UGT	UDP-glucuronosyltransferases
UMN	Upper Motor Neurons
US	United States of America
VAS	Visual Analogue Scale
WBC	White blood cell
WFN	World Federation of Neurology
WHO	World Health Organisation

\* It substitutes prior codification FAB122 (Ferrer Advanced Biotherapeutics 122)

## 1. SYNOPSIS

TITLE:	A multicenter, open-label extension study to investigate the long-term safety of FAB122 in patients with Amyotrophic Lateral Sclerosis
THE SPONSOR STUDY CODE:	FAB122-CT-2201
EudraCT NUMBER:	2022-003050-32
SPONSOR:	Ferrer Internacional, S.A. Barcelona, Spain
STUDY PHASE:	PHASE III Extension
STUDY DESIGN:	
Multicenter, multinational, open-label Phase III extension study to investigate the long-term safety of 100 mg FAB122 once daily as oral formulation in ALS patients.
 
All patients participating in the ADORE study will be invited to roll over to FAB122 and to participate in ADOREXT. Patients that discontinued treatment in the main ADORE study for other than safety reasons, will be also invited to re-start treatment with FAB122 in the OLE study. The duration of this open label extension (OLE) will be until the product is commercially available at each participant country, provided good tolerance and safety is proven. The sponsor could also make the decision to terminate the study at any time, in case the objectives of the main study (ADORE) are not met.
 
Patients not willing to continue receiving active treatment in the extension study or that had already discontinued study treatment during the course of the main ADORE study for safety reasons, will be asked to be contacted by phone and followed up for vital status.
 
Subjects rolling over active treatment will visit the clinic at Baseline (Visit 6 or 8 of the main study (+ 6 weeks in case the OLE is not fully set up) and every 3 months thereafter.

STUDY PARTICIPANTS:	
Study Population	ALS patients from main ADORE study
Inclusion Criteria	
Patients who meet all of the following criteria, will be eligible for the study:
 
 
1. who completed the full study period in the main ADORE study (FAB122-CT-2001);
 
2. whom the investigator has no concern and judges tolerable for receiving treatment with FAB122 from a risk and benefit point of view;
 
3. a female subject should not be able to become pregnant up to 30 days after the last dose of FAB122 and needs to meet at least one of the following criteria: 
 
- female subject who is not of reproductive potential is eligible
 
 
 

	
without requiring the use of contraception. A woman is considered not having childbearing potential when becoming post-menopausal unless permanently sterile. Permanent sterilisation methods include hysterectomy, bilateral salpingectomy and bilateral oophorectomy. A postmenopausal state is defined as no menses for 12 months without an alternative medical cause.
 
 
- female who is of reproductive potential and has a negative pregnancy test at baseline and is non-lactating. A female subject who is of reproductive potential agrees to use (or have their partner use) adequate birth control methods starting from the time of consent through 30 days after the last dose of study therapy. Longer periods of birth control may be required per local requirements. Acceptable methods of birth control include combined (estrogen and progestogen containing) hormonal contraception associated with inhibition of ovulation (oral, intravaginal, transdermal), progestogen-only hormonal contraception associated with inhibition of ovulation (oral, injectable, implantable), intrauterine device in place for ≥3 months, intrauterine hormone-releasing system, bilateral tubal occlusion or vasectomised partner.
 
 
4. a male patient must:
 
 
- agree he will not donate sperm during the period he will be using FAB122, AND use a condom during sexual intercourse with pregnant or non-pregnant women of childbearing potential (WOCBP) partner even if he is vasectomized and until 104 days after the last dose, .
 
- in addition WOCBP partner of the male patient must use the following acceptable methods of birth control during the study and until 104 days after the last dose: combined (estrogen and progestogen containing) hormonal contraception associated with inhibition of ovulation (oral, intravaginal, transdermal), progestogen-only hormonal contraception associated with inhibition of ovulation (oral, injectable, implantable), intrauterine device in place for ≥3 months, intrauterine hormone-releasing system, bilateral tubal occlusion or vasectomised partner;
 
 
5. providing informed consent.

Exclusion Criteria	
Patients who meet any of the following criteria, will not be eligible for the study:
 
 
1. Patient who has a medical condition (e.g. cardiac, pulmonary, gastrointestinal, musculoskeletal, or psychiatric illness) or personal circumstances which, in the opinion of the investigator, will make initiation or continuation of treatment with FAB122 not tolerable for them from a risk and benefit point of view.
 
2. Patient who discontinued study drug prematurely in the double-blind phase of the study (ADORE Study) for safety reasons.
 

	
3. Patient who has received any other investigational drug within the period between last visit of the main study and first visit of the extension study (i.e. another trial, managed access program, open label extension or early access program)
 
4. - History of known hypersensitivity to edaravone or to any of the excipients.
 
For patients who do not take FAB122 but are only followed up by phone, only inclusion criteria #1 and #5 will apply.

SAMPLE SIZE:	
No formal size calculation has been done for the extension study.
 
The main study plans to include approximately 300 patients. It is anticipated that 200-225 patients might be included in this extension study.

PLANNED STUDY PERIOD:	Approximately 3 years (up to the product is commercially available). Product commercialization is country dependent, thus study ending will differ between countries. The sponsor may terminate the study at any moment in case the objectives of the main study (ADORE) are not met)
STUDY SITES	Approximately 38 sites
OBJECTIVES AND OUTCOME MEASURES:	
PRIMARY OBJECTIVE:	To evaluate the long-term safety of FAB122 in patients with ALS.
SECONDARY OBJECTIVES:	
 
1. To evaluate the effect of treatment with FAB122 on overall survival;
 
2. To evaluate the effect of treatment with FAB122 on disease progression in patients with ALS;
 
3. To evaluate the effect of treatment with FAB122 on cognitive functioning;
 
4. To evaluate the effect of treatment with FAB122 on quality of life (QoL).
 

PRIMARY ENDPOINT:	Nature, frequency and severity of Treatment Emergent Adverse Events.
SECONDARY ENDPOINTS:	
 
1. Mortality-adjusted change from baseline in ALSFRS-R total score until the end of the study;
 
2. Overall survival, defined as time to death from any cause or respiratory insufficiency (insufficiency defined as tracheostomy or the use of non-invasive ventilation for <math>\geq 20</math> h per day for <math>\geq 10</math> consecutive days);
 
3. Change from baseline in SVC until the end of the study;
 
4. Mean change in norm-standardized ECAS total score;
 
5. Change from baseline in the total score on the ALS Assessment
 

	
Questionnaire-40-Item (ALSAQ-40) until the end of the study;
 
6. Change from baseline in EuroQoL – 5 Dimensions – 5 Levels (EQ-5D-5L) until the end of the study;
 
7. Change from baseline in Health related QoL Visual Analogue Scale (VAS) score until the end of the study;
 
8. Change from baseline in the prognostic ALS biomarker neurofilament light (NFL);
 
9. Change from baseline in the ALS biomarkers creatinine and creatinine kinase;
 
10. Change from baseline in the ALS biomarker Urinary extracellular domain of neurotrophin receptor p75 (Urinary P75ECD);
 
11. Change from baseline of oxidative stress biomarker 8-hydroxyguanosine (8-OHdG);
 
12. Cost-Utility analysis of treatment with FAB122.

SAFETY ENDPOINTS	
1. Parameters derived from vital signs and 12-lead electrocardiogram (ECG);
 
2. Parameters derived from laboratory tests (hematology, biochemistry, urinalysis);
 
3. Proportion of patients that drop out due to adverse events.

INTERVENTION(S):	
IMP(S):	
FAB122:
 
Fasted daily dose of 100 mg FAB122 granules for oral solution in single sachets, which has to be dissolved in 100 mL water prior to administration.

STATISTICAL METHODS:	
All treatment emergent AEs (TEAE) will be coded using the Medical Dictionary for Regulatory Activities (MedDRA version 23.0) coding dictionary. And all preferred terms (PT) will be tabulated by System organ Class (SOC) and additional tabulations will be made by severity and drug relatedness. A separate table (or listing) will be created for serious TEAEs (SAE).
 
Safety variables will be tabulated and presented for all subjects in the Safety Population. Data will be summarized by treatment and time. Exposure to study drug and reasons for discontinuation of study drug will be tabulated.
 
Difference in survival curves will be evaluated using a log-rank test, stratified for randomization factors. The effect of treatment will be expressed as hazard ratio. In case of non-proportional hazards, we will estimate the difference in restricted mean survival time (RMST).
 
Changes in the ALSFRS-R score, ALSAQ-40, SVC, EQ-5D-5L, and VAS

	score over time will be presented descriptively.
--	--

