### **3. OBJECTIVES AND OUTCOME MEASURES**

#### **3.1. Objectives**

##### **3.1.1. Primary Objective**

To evaluate the long-term safety of FAB122 in patients with ALS.

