### **11.3.5. Safety Analysis**

Safety evaluations will be based on the incidence, severity, and type of AEs and clinically significant changes in the subject's physical examination findings, vital signs, and clinical laboratory results. Safety variables will be tabulated and presented for all subjects in the Safety Population. Data will be summarized by treatment and time. Exposure to study drug and reasons for discontinuation of study drug will be tabulated.

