#### **11.3.5.2. Adverse Events**

All treatment emergent AEs (TEAE) will be coded using the Medical Dictionary for Regulatory Activities (MedDRA version 23.0) coding dictionary. And all preferred terms (PT) will be tabulated by System organ Class (SOC) and additional tabulations will be made by severity and drug relatedness. A separate table (or listing will be created for serious TEAEs (SAE).

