#### **11.3.5.4. Laboratory Parameters**

Clinical laboratory tests (including re-check values if present) will be listed chronologically. 'H' and 'L', denoting values above or below the investigator reference range (when present), will flag out-of-range results. At each time point, absolute values and change from baseline of the hematology and chemistry variables will be summarized by treatment and time with n, mean, SD, SEM, median, Min, and Max values. The categorical data of the urinalysis will be summarized by treatment and time in frequency tables by variable.

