### 5 STATISTICAL ANALYSIS

#### 5.1 General considerations

Appropriate rounding will be performed for the summary statistics: arithmetic mean, median, SD (standard deviation) and confidence limits will be presented with one more decimal than the original data; minimum and maximum values will be presented with the same precision as the original data. In frequency tables, percentages will be presented with 1 decimal. P-values will be presented with 3 decimals, and those smaller than 0.001 will be replaced by <0.001.

Descriptive statistics presented in general summary tables will be the number of non-missing observations (n), mean, SD, minimum, median and maximum for quantitative data. For categorical data, frequency counts and percentages will be determined. The denominator when calculating percentages will be the number of patients in the applicable analysis population. Descriptive statistics will be displayed for all visits that a measurement is collected on, even if the endpoint is only referring to limited visits for the analysis.

Baseline is defined as the last value measured prior to first study treatment administration in ADOREXT study, unless otherwise specified. Typically, baseline data are collected at Visit 6 or 8 of the ADORE study. In case this value is missing for a specific patient in ADOREXT CRF data, but an earlier measurement is collected in ADORE study data, this value will be used as baseline instead. Unscheduled measurements are excluded as baseline value.

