### **5.6.1 Adverse events**

A treatment emergent adverse event (TEAE) is defined as an adverse event that appears at or after first dosing of extension. In case of (partially) missing start/stop dates, refer to Section [5.2](#).

An AE overview table will be created displaying the number of patients (and percentage) experiencing a treatment-emergent adverse event (TEAE) and the number of TEAEs for: any TEAE, any mild/moderate/severe TEAE, any unrelated/related TEAE, any serious AE, any serious TEAE, and any TEAE leading to study treatment discontinuation, any AE leading to death.

All TEAEs and those leading to death will be tabulated. SUSARs will be reported by the pharmacovigilance vendor.

All TEAEs are tabulated by System Organ Class (SOC) and Preferred Terms (PTs) within each SOC according to the MedDRA terminology list. TEAEs will be tabulated using frequency counts (number of patients with at least one event, and number of events) and percentage of patients with the event. Similar tables will be created for TEAEs leading to premature treatment discontinuation and Serious TEAEs. These summary tables will be presented by decreasing frequency of occurrence based on SOC and PT.

For summary tables, an AE is considered related if the causality to the study medication is classified as either ‘Probably Related’ or ‘Possibly Related’, where a missing relationship is also considered related. Otherwise, it will be considered unrelated for summary tables.

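### The protocol plans safety summaries by time and an exposure table; the SAP's TEAE tables are cumulative only, so they cannot show whether risk changes with duration of FAB122 use, and SAP section 6 does not name the omission.

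*Protocol*

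**What the plan says.** **Protocol.** The primary objective (3.1.1) is: "To evaluate the long-term safety of FAB122 in patients with ALS". The Synopsis and section 11.3.5 state for safety variables: "Data will be summarized by treatment and time". Section 11.3.5 adds: "Exposure to study drug and reasons for discontinuation of study drug will be tabulated". The adverse event subsection (11.3.5.2) plans tables by system organ class and preferred term, and "additional tabulations will be made by severity and drug relatedness". It names no time interval. Laboratory section 11.3.5.4 does carry the time wording: "chemistry variables will be summarized by treatment and time".

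**SAP.** Section 5.6.1 starts the clock at the extension for everyone: "A treatment emergent adverse event (TEAE) is defined as an adverse event that appears at or after first dosing of extension". On content it says: "TEAEs will be tabulated using frequency counts (number of patients with at least one event, and number of events) and percentage of patients". On the denominator, section 5.1 says: "The denominator when calculating percentages will be the number of patients in the applicable analysis population". Tables 14.3.1.1 to 14.3.1.4 in section 9.3 are an overview, TEAEs, serious TEAEs and TEAEs leading to discontinuation. Their titles and the text of 5.6.1 mention no onset interval, person-time or time to onset. Section 3.1.2 says safety data will also be shown by ADORE randomised group. Other safety endpoints (5.6.2) and dosing (5.7) are out of scope after early termination. Section 6 says in general terms that some planned analyses are dropped.

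**The concern.** Long-term safety includes the question of whether risk rises, falls or stays level as treatment continues. The protocol itself raises a toxicity for which duration could matter: section 2.2 reports that the DSMB looked specifically at potential neurotoxicity, and section 8.2.1 directs the neurological examination at peripheral nerve dysfunction.

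A cumulative percentage over all dosed patients answers this only if everyone is followed for the same time, and even then it gives one point on a curve. Here follow-up is unequal. Patients leave ADORE after 48 to 72 weeks, baseline may be up to 6 weeks later, the country protocol versions listed in the SAP are dated from 24 January to 10 July 2023, and the study stopped early. Late-onset events are therefore divided by many patients who were never observed that long. Without an exposure table, a reader cannot compute even a crude rate.

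**Working it through.** The documents give no AE rate, power or follow-up distribution, so there is no planned figure to reproduce. The check has four parts.

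**1. Commitments against the SAP**

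| Protocol 11.3.5 | SAP |
|---|---|
| Safety variables by treatment and time | By ADORE group (3.1.2); no time dimension in 5.6.1 or 9.3 |
| Exposure to study drug tabulated | 5.7 out of scope; no exposure table in 9.3 |
| Reasons for stopping study drug | Partly kept: reasons for leaving the extension, in disposition (5.4.3) |
| Laboratory, ECG and vital signs over time | 5.6.2 out of scope |

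Section 6 does not name the by-time summaries or the exposure table among the losses.

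**2. What a cumulative percentage hides, with equal follow-up**

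Assume 20% of patients have a given TEAE by month 12 and nobody is censored. Let F(t) = 1 − exp(−H(t/12)^k), with H = −ln(0.80), so F(12) = 20% for every k. First onset by quarter, as a percentage of patients enrolled:

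| Hazard | 0–3 mo | 3–6 | 6–9 | 9–12 | Planned table |
|---|---|---|---|---|---|
| Falling (k = 0.5) | 10.6 | 4.0 | 3.0 | 2.4 | 20% |
| Constant (k = 1) | 5.4 | 5.1 | 4.9 | 4.6 | 20% |
| Rising (k = 2) | 1.4 | 4.0 | 6.4 | 8.2 | 20% |

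The same happens at an assumed 10% or 40%.

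**3. Adding unequal follow-up**

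Assumptions: 200 patients (low end of the anticipated 200–225), follow-up uniform over 0 to T months, eight first events, and person-time not cut at the event. T = 15 approximates the 14.8 months from the earliest protocol version listed in the SAP (24 January 2023) to the SAP date (19 April 2024). T = 18 approximates protocol version 1.0 (17 October 2022) to the same date. These are not dosing dates, and the study had already been terminated when the SAP was finalised, so T = 12 is shown as well.

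- Total patient-years = 200 × (T/2)/12
- Patients reaching month 6 = 200 × (T − 6)/T
- Patient-years after month 6 = 200 × [(T − 6)²/(2T)]/12

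| T (months) | Total PY | PY after month 6 | Reach month 6 | Planned table | Overall per 100 PY | After month 6 per 100 PY, if all 8 are late |
|---|---|---|---|---|---|---|
| 12 | 100 | 25 | 100 | 4.0% | 8.0 | 32.0 |
| 15 | 125 | 45 | 120 | 4.0% | 6.4 | 17.8 |
| 18 | 150 | 66.7 | 133 | 4.0% | 5.3 | 12.0 |

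At T = 15 a constant rate would put 80 × 0.064 = 5.1 events before month 6 and 45 × 0.064 = 2.9 after it. The all-late case puts 0 and 8, and 8/120 = 6.7% of those reaching month 6. Both cases print 8/200 = 4.0%, and both give 6.4 per 100 patient-years overall, so a single overall rate would not separate them either.

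This example runs on extension time and pools both ADORE groups. It shows what pooling over time conceals, not an expected FAB122 effect.

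**4. What the ADORE-group columns can show**

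Take 200 to 225 patients, two-sided 5%, and placebo:FAB122 splits of 1:1 and 1:2 (assumed, because neither document states the ratio). Power to separate former-placebo from former-FAB122 patients is 0.67–0.72 for 10% against 2%, 0.50–0.56 for 20% against 10%, and 0.13–0.14 for 25% against 20%.

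**The case against.** The strongest reply is that the by-time sentence is general. Section 11.3.5.2, which deals with adverse events specifically, names no interval, and the explicit by-time wording sits with weight and BMI, laboratory and urinalysis data. That stands: a reader might infer that the SAP breaks a specific promise of AE tables by onset interval, and the documents do not support that. What they support is that the general commitment and the exposure table have no counterpart in the SAP.

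A reader might also infer that an excess at first exposure in former-placebo patients would be invisible. It would not. SAP 3.1.2 shows safety by ADORE group, so a large excess could appear as a difference between columns. A small one would probably be missed, and timing is lost in either case. The columns are also not a clean comparison: patients who stopped study drug in ADORE for safety reasons cannot be dosed in the extension, so the former-FAB122 group is selected for having tolerated FAB122.

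Three further points limit the concern.

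- The tables give more than one percentage. Event counts, severity, relatedness, seriousness and discontinuation are there, and death has a Kaplan-Meier analysis, though in the mITT set.
- An item called TEAEs (14.3.2.2) is planned and might show onset dates, but its columns are not stated and section 9.4 puts listings out of scope.
- The SAP says openly and repeatedly that early termination reduced its scope. That explains a shorter report. It does not make onset intervals impractical: onset dates are collected (Protocol 9.5), and the SAP already compares them with first-dose dates to classify TEAEs (5.2).

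Finally, intervals counted from the first extension dose would be the wrong clock for a pooled column. The first three months are first exposure for one group, and follow 48 to 72 weeks in ADORE for the other. This stands and shapes the fix.

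**Conclusion.** The planned TEAE tables cannot show whether risk changes with duration of FAB122 use, which is a real gap for a primary objective of long-term safety. The exposure data needed for even a crude rate are also dropped, and section 6 names neither loss. In the illustration, the same printed 4.0% can conceal a late rate of 12.0 to 32.0 per 100 patient-years against 5.3 to 8.0 overall. Those figures rest on assumed follow-up, group size and event counts, and are not predictions. The stronger claims, that first-exposure effects cannot be seen at all or that onset-interval AE tables were specifically promised, are not supported.

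**What to change.** In SAP 5.6.1 and 9.3, add versions of the TEAE overview, serious TEAEs, TEAEs leading to discontinuation and common preferred terms (for example those in 5% or more of patients) by onset interval.

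- **Clock.** Time since first FAB122 dose: the first ADORE dose for former-FAB122 patients and the first extension dose for former-placebo patients. State how time off drug is handled, both for the gap before extension baseline and for patients who stopped in ADORE and restart.
- **Layout.** Show the two ADORE groups separately and do not pool them on the extension clock.
- **Denominator.** Patients under observation in the extension at the start of each interval, allowing for late entry of former-FAB122 patients, whose extension time begins only after 48 to 72 weeks in ADORE. Add person-time and exact 95% confidence intervals.
- **Sparse intervals.** Merge them, for example into a single interval beyond month 6 for former-placebo patients. With T = 15, only 200 × 3/15 = 40 patients pass month 12 of the extension, contributing 200 × [3²/(2 × 15)]/12 = 5 patient-years, so a separate row beyond month 12 would say little.
- **Exposure and disclosure.** Restore a short summary of duration of exposure by ADORE group. In section 6, list any by-time safety summaries that remain dropped, with the reason.

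The cost is SAP wording and one or two more tables from dates already held. The downside is wide confidence intervals in the later periods, which the tables would then show openly.
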